**Figure 1. Study process**

## 5. Study Population

### a. Number of Subjects

State the number (or approximate number, if appropriate) of subjects you plan to include at the KP region to which this study is being submitted. If applicable, distinguish between the number

of subjects who are expected to be enrolled/screened and the number of subjects needed to complete the research procedures (e.g. numbers of subjects excluding screen failures).

As appropriate, consider different populations of subjects within the same study (e.g. subject/caregiver, parent/child, patient/physician). If this is a multicenter study, indicate the total number of subjects to be accrued across all sites.

This study is an educational intervention with two arms: a research interventionist guided PSMOT (with a sub-arm of patients who decide to taper their medications) or control group (no intervention, usual care). We plan on enrolling 250 participants. 125 participants in each arm. Eligible participants will be randomized based on their KPW primary care clinic and baseline opioid dose into either arm.

	Invited (contacted)	Enrolled
KP Washington	825	250
Other sites	-	-
Total	825	250

b. Inclusion and Exclusion Criteria

- Describe the criteria that define who will be included or excluded in your final study sample.
- Describe how individuals will be screened for eligibility.
- Describe the plan for disposition of data collected during recruitment/screening in the event of a screen failure or when a potential subject is contacted but declines participation (e.g. destroyed immediately, destroyed at end of study, retained for separate analysis or so that subjects are not contacted repeatedly about participation after they have declined, etc.).

Inclusion Criteria:

KPW enrollees:

- age 18-80 years (*from KPWHR Virtual Data Warehouse (VDW)*)
- receiving care at a KPW primary care clinic (*from VDW*)
- with chronic non-cancer pain (CNCP), defined as patient-reported pain on more than half the days in the past 6 months (*from eligibility screening*)
- currently on higher-dose LtOT, defined as >90 days' supply in the past 180 days with a mean daily dose of 40 mg morphine equivalent dosing (MED) or greater in the past 90 days, as first identified via KPW's pharmacy dispensing data and opioid use subsequently validated by patient self-report during screening for the trial (*from VDW*)

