##### **a. Data Analysis**

Describe the data analysis plan, including:

- Statistical procedures.
- When applicable, the power analysis.
- Any procedures that will be used for quality control of collected data.

We will use descriptive statistics to characterize the sample at baseline. To address the trial's effectiveness aims, we will use an intent-to-treat approach (i.e., individuals will be analyzed according to randomized group regardless of participation in any opioid taper support sessions). We will also use a complete case analysis (i.e., that includes those participants who have observed follow-up outcome data) since we expect at least 85% follow-up at 12 months (primary time-point).

To compare each of the primary outcome measures (opioid dose and PEG score) between intervention groups the following linear regression model will be constructed:  $E(Y_{ij}) = \beta_0 + \beta_1 Trt_i + \beta_2 Time_j + \beta_3 Trt_i \times Time_j + \alpha_z Z_i$ , where  $Y_{ij}$  is the outcome for person  $i$  at time  $j$  ( $j=6$  or 12 months),  $Trt_i$  is the dichotomous intervention effect of interest (with control arm as the referent group),  $Time_j$  is the dichotomous variable indicating the 6- or 12-month time point,  $Trt_i \times Time_j$  is the interaction between the treatment and time point indicators and  $Z_i$  is a vector of baseline covariates that we a priori plan to adjust for including age, gender, baseline opioid dose group, whether they were referred to COMET, and KPWA clinic. We will include both 6- and 12-month time-points in a single model to improve statistical efficiency, but the 12-month time point is considered primary. We will fit the linear regression model using GEE with robust standard errors to account for the multiple time points in a single model. We will use two-sided tests at the 0.05 level. Arguments against adjusting for multiple comparisons for two co-primary outcomes have been made by Rothman and others. (Rothman KJ. No adjustments are needed for multiple comparisons. *Epidemiology*. 1990;1:43–46) For each outcome, we will report the adjusted mean difference between treatment groups and its 95% confidence interval.

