**Sample Size:**

Our sample size is designed to ensure that we are highly powered to detect a clinically meaningful difference in the co-primary outcomes of opioid dose and pain (PEG) at 12 months. With 172 participants (86 per intervention arm) we will have >90% power to detect a 20mg mean difference in opioid dose between intervention groups assuming a 34 mg SD (based on data from KPWHRI participants meeting entry criteria) and a two-sided, two-sample equal-variance t-test. Assuming the mean baseline dose in our study population to be 67mg MED, this 20mg difference represents a clinically meaningful 30% reduction. Further, given our

sample size of 172 participants we will have approximately 90% power to detect a 1.2 point difference in the PEG between intervention groups, assuming a standard deviation of 2.5. To ensure adequate power given potential loss to follow-up we inflated our final sample size by 25% yielding a target randomization of 215 participants. This will also allow some pre-specified sub-group analyses to look for heterogeneity of treatment effect, as described below. Sample and power calculations were conducted using PASS software Version 14.

b. Sharing of Results with Subjects

Describe whether results (study results or individual subject results, such as results of standard or research lab tests and genetic tests) will be shared with subjects or their providers.

If the study carries a risk of incidental findings, describe your plan for evaluating these and determining whether and how subjects or their providers will be given this information.

If laboratory results will be shared with subjects or their healthcare providers, verify that the laboratory conducting the test is Clinical Laboratory Improvement Amendments (CLIA) certified. We will not be sharing study results with participants

We will be communicating some study information with providers, however we will not be sharing study results with the provider

- If a participant is enrolled in the intervention arm, the provider will be notified of their participation by the study team

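### The opioid dose model adjusts for baseline dose only as an undefined group, although the continuous baseline dose is already held, so the 12-month estimate gives up some precision

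*Combined protocol and SAP*

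**What the plan says.** Section 6.a (Data Analysis) fits one linear model by GEE to the 6- and 12-month outcomes, with 12 months primary. Baseline is not an outcome row, so baseline dose can enter only through the covariates. These are listed as including "age, gender, baseline opioid dose group, whether they were referred to COMET, and KPWA clinic". The section does not define the dose groups.

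The inclusion criteria (Section 5.b) require long-term opioid therapy "with a mean daily dose of 40 mg morphine equivalent dosing (MED) or greater in the past 90 days", identified first from pharmacy dispensing data. Section 2 lists percent dose reduction from baseline as an outcome, which also needs each participant's own baseline dose. Section 4 says that randomisation takes account of clinic and baseline opioid dose.

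The Sample Size paragraph states: "With 172 participants (86 per intervention arm) we will have >90% power to detect a 20mg mean difference in opioid dose", "assuming a 34 mg SD (based on data from KPWHRI participants meeting entry criteria) and a two-sided, two-sample equal-variance t-test". It gives the population mean as follows: "Assuming the mean baseline dose in our study population to be 67mg MED".

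Section 6.a also plans, for every outcome, a sensitivity analysis that adds further baseline factors if they predict the outcome, predict missingness or differ between arms. Continuous baseline dose is not named there.

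**The concern.** The baseline value of an endpoint is usually its strongest predictor. A group term uses only the differences between groups and discards all variation in dose within a group. Eligibility starts at 40 mg, and a mean of 67 mg with an SD of 34 mg implies a long right tail. Any group that is open at the top would therefore pool quite different doses. If follow-up dose tracks baseline dose within groups, that variation stays in the residual, and chance imbalance within a group adds noise to the mean difference in mg. At stake is the width of the 95% confidence interval for one of the two co-primary outcomes. The plan gives no reason for leaving out a value that it already holds.

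**Working it through.** **1. The plan's own figure.** Inputs from the Sample Size paragraph and Section 6.a: 86 per arm, difference 20 mg, SD 34 mg, two-sided 0.05.

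- SE = 34 × √(2/86) = 5.18 mg, and 20/5.18 = 3.86.
- Power ≈ Φ(3.86 − 1.96) = Φ(1.90) = 97.1%. The exact noncentral t gives 97.0%.

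This agrees with the stated figure of more than 90%. It uses no covariate, so the promised power does not depend on how baseline dose is adjusted for.

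**2. Formula for the loss.** Let ρ be the correlation between baseline and follow-up dose, and η² the share of baseline-dose variance that lies between groups. With a linear relation:

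- residual variance with continuous dose: 34² × (1 − ρ²)
- residual variance with the group only: 34² × (1 − ρ²η²)
- variance ratio: (1 − ρ²η²)/(1 − ρ²)

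**3. Assumptions.** The documents give neither ρ nor the cut-points. Two groupings were tried, both taken from elsewhere in the protocol: the four bands of Table 1 at or above 40 mg (cuts at 50, 90 and 120), and a split at 90 mg as in the subgroup list of Section 6.a. η² was simulated from right-skewed distributions that start at 40 mg with mean 67 mg (shifted lognormal and gamma with SD 34, shifted exponential with SD 27). It is about 0.71-0.85 for the four bands and 0.53-0.65 for the split. The 34 mg SD is used for follow-up dose, as in the plan.

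Example, ρ = 0.7:

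- four bands, η² = 0.713: (1 − 0.49 × 0.713)/(1 − 0.49) = 0.651/0.51 = 1.28
- split at 90, η² = 0.649: (1 − 0.49 × 0.649)/0.51 = 0.682/0.51 = 1.34

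**4. Variance with the group only, relative to continuous dose.**

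| ρ (assumed) | Formula, four bands | Formula, split at 90 mg | Simulated trials, 172 evaluable (four bands to split at 90) |
|---|---|---|---|
| 0.3 | 1.02-1.03 | 1.03-1.05 | 1.02-1.05 |
| 0.5 | 1.05-1.10 | 1.12-1.16 | 1.06-1.14 |
| 0.7 | 1.15-1.28 | 1.34-1.45 | 1.13-1.39 |
| 0.8 | 1.27-1.51 | 1.62-1.83 | 1.28-1.84 |

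Formula and simulation agree to within a few points. At ρ = 0.9 the formula gives 1.65-2.22 (four bands) and 2.49-3.00 (split at 90). These groupings do not bound the loss: a single cut at 50 mg has η² of only 0.16-0.33 and gives 1.65-1.81 at ρ = 0.7.

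**5. In mg.** The 95% half-width is 1.96 × 5.18 = 10.2 mg unadjusted.

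- ρ = 0.7: 7.3 mg with continuous dose (10.2 × √0.51), 7.8-8.2 with four bands, 8.4-8.7 with the split. The cost is 0.5-1.4 mg.
- ρ = 0.8: 6.1 mg with continuous dose (10.2 × 0.6), 6.9-7.5 with four bands, 7.8-8.3 with the split. The cost is 0.8-2.2 mg.

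**6. Power.** For 20 mg and ρ of at least 0.5, power is at least 98.4% with either grouping and at least 99.3% with continuous dose.

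**The case against.** **Nothing the trial promised is lost.** Power for 20 mg is about 97% before any adjustment, and the cost is at most about 2 mg of half-width at correlations up to 0.8. This stands. A reader might infer that the dose comparison is biased or underpowered, but the plan's own figures rule that out. Precision still has value, because the plan reports the adjusted difference with its interval, and subgroup effects with acknowledged reduced power. The true effect may also be smaller than 20 mg: the pilot's 43% against 19% reduction, applied to 67 mg, is 0.24 × 67 = 16 mg.

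**The size rests on assumptions.** This also stands. A reader might infer a loss that is large in any case. Simulating percentage reductions from baseline at 172 evaluable gives variance ratios of 1.17-1.62 (four bands) and 1.33-1.97 (split at 90). But that construction builds in strong tracking, with within-arm correlations of roughly 0.59-0.87. No passage states such a correlation, and voluntary tapers that can be paused (Section 6, intervention arm) could weaken it. Nor does any passage say that the Table 1 bands or the 90 mg split define the model's groups. The calculations also use least squares at one time point, not the planned two-point GEE with all covariates.

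**The group term has a purpose.** A reader might infer that it should go. Randomisation takes account of baseline dose, so the group may be the randomisation factor. It also avoids assuming linearity in a skewed distribution. That is a reason to keep it, not a reason to omit the continuous value.

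**The plan may already cover it.** The covariate list is open-ended, and the sensitivity analysis could add continuous dose. Neither names it, and the sensitivity analysis leaves the primary estimate unchanged.

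**Conclusion.** The point holds as a matter of efficiency only. As written, the primary dose model uses baseline dose through an undefined group and leaves out the mg value held for every participant. With 172 evaluable participants, the variance of the 12-month dose contrast is larger than with continuous dose by about 2-5% at an assumed correlation of 0.3, 6-14% at 0.5, 13-39% at 0.7 and 28-84% at 0.8. In each range the lower end is the four Table 1 bands and the upper end the split at 90 mg. The direction is secure whenever baseline and follow-up dose are correlated within groups. The size is not, because it depends on the correlation, the cut-points, a linear relation and the assumed shape of the dose distribution. The planned power is unaffected.

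**What to change.** In Section 6.a, name continuous baseline mean daily dose (mg MED, from the same 90-day dispensing window as eligibility) as a prespecified covariate in the opioid dose model. Keep the dose-group term where it reflects the randomisation factor, and state its cut-points.

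The cost is one covariate in the analysis plan, with no new data, participants or procedures. Under a linear relation, keeping both terms raises the variance by at most about 3% compared with continuous dose alone.

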**2. Objectives**

Describe in plain language the purpose, specific aims, or objectives and indicate the primary goal(s) of the study (e.g. safety, tolerability, effectiveness, feasibility, pilot study, etc.). State the hypotheses to be tested. State primary and any secondary study endpoints.

This study will adapt and test a University of Washington (UW) developed/piloted pain self-management training for prescription opioid taper intervention at Kaiser Permanente Washington (KPW). To address patients' fears of opioid taper that limited recruitment into our pilot study, we will begin with randomization to pain self-management training and then offer the option of self-paced opioid taper: *Pain Self-Management Training for Opioid Taper* (PSMOT). The optional taper will occur through recommendations from the research interventionist the patient's primary care provider (PCP). This study aims to enroll 250 participants and randomize them into either 1) a nurse or physician assistant research interventionist guided PSMOT or 2) regular care (no intervention). Specifically, we will test the effectiveness of this intervention, compared with control group on opioid dose and pain outcomes among patients on high dose ( $\geq$  40 mg morphine equivalent dose) long-term opioid therapy (LtOT) for chronic non-cancer pain (CNCP) in a pragmatic randomized trial.

The objectives of this study are:

- To adapt our previously developed prescription opioid taper support intervention by a physician assistant into a telephone-delivered pain self- management training that provides the option for supported opioid taper (PSMOT) through the patient's PCP. We will recruit participants who receive care from multiple primary care clinics. The intervention will be administered by a KPWA research interventionist (a physician assistant or registered nurse) who will be trained and supervised by a UW pain psychiatrist and UW research clinician and will include guidance in opioid and non-opioid medication prescribing. This training and guidance will be consistent with KPWA guidelines.

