1. Recruitment screening where the Survey Research Program interviewers call to recruit participants and screen them into the study with simple screening questions.
2. Pre-randomization screening where a research specialist will screen for sensitive ineligibility criteria such as psychiatric hospitalization and recent suicidal ideation.

Both screening scripts and screening questions are included in this packet.

All participant contact information (name, address, telephone number) and their study disposition (non-responder, refuser, or ineligibility reason) remains in the study recruitment database for the duration of the study to ensure that the participant isn't contacted for recruitment again.

The aggregate table below will be populated each time a potentially eligible sample is pulled from the VDW (twice per month) and prior to attempting any contact (i.e., mailing of letters and phone calls) with subjects. This table will be used for sample monitoring and a future non-responder bias analysis. The table will be updated twice a month with potentially eligible subjects moving into columns of enrolled, non-responder, active refuser, or ineligible.

**Table 1.** Characteristics to be summarized and updated every two weeks when new potentially eligible subjects are identified from the KPWHRI Virtual Data Warehouse (VDW).

	Potential eligible (VDW data only)	Enrolled	Not enrolled (active and passive refusers)*
	n=	n=	n=
%			
Mean age (SD), years			
% Male			
Race			
White			
Black			
Asian			
Other			
Missing			
Hispanic			
Prior health plan enrollment, years			
1-2			
3-9			

10+			
Mean number (SD) of visits with a pain diagnoses, past year			
Multifocal pain (pain arising from >1 location)			
Mean daily opioid dose, past 90 days (MEQ - morphine equivalent dose)			
<40 MEQ			
40-49 MEQ			
50-89 MEQ			
90-119 MEQ			
120+ MEQ			
Primary Care Clinic			
Clinic 1			
Clinic 2			
Clinic 3			
Etc.			
Charlson co-morbidity index, past year			
0			
1			
2+			
Depression diagnosis, past year			
Anxiety diagnosis, past year			
Substance use disorder, past year			
Smoking status, past year			
Current			
Past			
Non-smoker			

c. Vulnerable Populations

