A set of comparable linear regression models will be fit for continuous secondary outcomes. For dichotomous secondary outcomes, similar models will be built using a modified Poisson regression framework with a robust sandwich estimator to estimate adjusted relative risks and 95% confidence intervals. In addition, for each outcome, we will conduct a sensitivity analysis that further adjusts for baseline factors that are predictive of the outcomes, predictive of the probability of being missing at follow-up, or found to be significantly different between treatment groups. If more data are missing than expected (i.e., <85% with follow-up), we will also conduct a sensitivity analysis using an imputation method for non-ignorable non-response to evaluate whether our results are robust to different missing data assumptions. Selection bias analyses will compare demographic and clinical data of non-responders (potentially eligible per VDW and unreachable for recruitment) with responders (enrolled) using chi square and t-tests. This will allow us to identify factors associated with non-response. Secondary analyses will be conducted to assess for subgroup heterogeneity of treatment effects across levels of these pre-specified baseline variables: SUD+ vs SUD-, MH+ vs MH-, <90mg. vs >90mg MED, opioids with sedatives vs without, and focal pain vs multifocal pain. Heterogeneity will be indicated by a significant test of the interaction between treatment and each baseline variable, and subgroup-specific treatment effects with confidence intervals will be reported. In light of multiplicity and reduced power, these results of these analyses will be interpreted cautiously.

---

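### As worded, the selection-bias comparison in section 6.a puts people who were reached and declined in neither group, which conflicts with the dispositions and Table 1 in section 5.b

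*Combined protocol and SAP*

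**What the plan says.** The documents describe the non-enrolled group in three ways.

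- **Section 6.a, Data Analysis.** The selection-bias analyses compare "non-responders (potentially eligible per VDW and unreachable for recruitment) with responders (enrolled) using chi square and t-tests". The stated aim follows: "This will allow us to identify factors associated with non-response".
- **Section 5.b, text before Table 1.** The table is refreshed twice a month, with "potentially eligible subjects moving into columns of enrolled, non-responder, active refuser, or ineligible". Its purpose is given as well: "This table will be used for sample monitoring and a future non-responder bias analysis". Each person's "study disposition (non-responder, refuser, or ineligibility reason) remains in the study recruitment database for the duration of the study".
- **Section 5.b, Table 1 itself.** There are three columns: potentially eligible, enrolled, and one headed "Not enrolled (active and passive refusers" (the heading closes the bracket and carries an asterisk). There is no separate column for active refusers and none for people found ineligible.

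Section 2 (Objectives) explains that the trial was redesigned because of "fears of opioid taper that limited recruitment into our pilot study". Section 3.b (Preliminary Data) names recruitment as the main barrier to feasibility. On scale, section 5.a states "We plan on enrolling 250 participants", against 825 invited.

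**The concern.** An analysis labelled as addressing selection bias should cover the routes by which potentially eligible people fail to enrol. One of these is active refusal, and section 6.a does not include it. The omission is notable because the plan itself expects recruitment to be hard and codes refusal as a distinct outcome.

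At stake is what the report can say about applicability. If enrollees resemble the unreachable but differ from those who declined, the tests as specified would show little, and a reader could take that as reassurance about selection in general. The two sections also leave the analyst without a single instruction. Following section 6.a drops the refusers. Following the Table 1 heading keeps them, but merges them with people who never responded.

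**Working it through.** No sample size, power or alpha figure bears on this point, so there is no stated figure to reproduce. The check is of the text, with simple arithmetic for scale.

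**Step 1: place each disposition in each version of the comparison.**

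| Disposition (section 5.b) | Section 6.a tests | Table 1 |
|---|---|---|
| Enrolled | Responder group | Enrolled column |
| Unreachable or passive non-responder | Non-responder group, if unreachable | Pooled not-enrolled column |
| Active refuser | In neither group | Pooled not-enrolled column |
| Ineligible at screening | In neither group | No column shown |

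The active-refuser row is the conflict. Table 1 includes the group and the formal tests do not, although the table is said to serve the non-responder analysis and section 6.a is the only place where such an analysis is specified.

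**Step 2: size of the non-enrolled group.** Inputs from section 5.a: 825 invited, 250 enrolled.

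825 − 250 = 575 not enrolled; 575 / 825 = 69.7%.

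**Step 3: how many could fall outside the tests.** The documents do not divide the 575. Assume for now that none are ineligible and let u be the unreachable share. The number who were reached and declined is 575 × (1 − u):

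- u = 25%: 575 × 0.75 ≈ 431
- u = 50%: 575 × 0.50 ≈ 288
- u = 75%: 575 × 0.25 ≈ 144

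People found ineligible reduce these counts in proportion. If a fifth of the 575 were ineligible (again an assumption), the base would be 575 × 0.8 = 460 and the counts would be 345, 230 and 115. These figures treat 825 as the number sent an invitation. The column is also labelled as contacted; if that means reached by telephone, the unreachable would lie outside the 825 and the split would change.

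**Step 4: why pooling is only a partial answer.** Let d_R be the difference between active refusers and enrollees on some characteristic, and d_U the difference between the unreachable and enrollees. The pooled comparison sees

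(1 − u) × d_R + u × d_U.

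In the limiting case d_U = 0, the section 6.a test sees nothing and the pooled Table 1 column shows 75%, 50% or 25% of d_R for u = 25%, 50% or 75%. This case shows what each layout is able to detect. It is not evidence that refusers in this trial differ.

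**The case against.** The strongest reply is that the plan does not ignore refusers. Table 1 sets them, pooled with passive non-responders, beside enrollees on opioid dose, age, sex, race, pain, clinic, comorbidity, depression, anxiety, substance use and smoking, and is linked to the bias analysis. Refusal status is kept throughout the study. Section 6.a promises only to find factors associated with non-response, and section 5.b treats a non-responder as distinct from an active refuser, so the sentence can be read as deliberately narrow. It sets no rule for concluding that selection is small. All of this stands, and it confines the point to a mismatch between the two sections. It does not remove the mismatch, because the formal tests still omit a group that the plan tracks.

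A reader might also infer that fear of taper makes active refusers the only informative group. The documents do not support that. Section 5.k and the sequential description in section 6 show that everyone is mailed a letter and information sheet about the study before any call, so someone who cannot be reached may have read the offer and be avoiding the telephone. The term passive refuser in Table 1 allows for this. Section 2 reports fear of taper as a limit on the pilot and presents the present design as the response to it. No section says why people decline this trial, or that reasons for refusal are recorded.

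**Conclusion.** The point holds as an inconsistency of low severity. Read as written, section 6.a excludes people who were reached and declined, while section 5.b tracks them and Table 1 pools them with passive refusers. The formal tests could therefore miss differences between enrollees and active refusers. The group outside the tests might number from roughly 144 to 431 of the planned 575, under an assumed unreachable share of 75% to 25% with no ineligibles, and fewer once ineligibles are removed. The documents give no actual split.

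Two stronger readings should be resisted. First, the trial's effect estimates are not biased by this. It is a descriptive check on who enrolled, and the randomised comparison, the co-primary analyses, power and alpha do not depend on it. Second, a comparison with refusers would not show whether the result applies to patients unwilling to taper. People may decline for many reasons, and no Table 1 variable measures willingness to taper.

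**What to change.** In section 6.a, redefine the selection-bias analysis so that enrolled participants are compared, on the Table 1 variables, with two separate groups: (a) active refusers, meaning people who were reached and declined at either call, and (b) unreachable or passive non-responders. Report people found ineligible at screening as a separate group, outside both comparisons. In section 5.b, split the Table 1 not-enrolled column in the same way and add a column for ineligibles, so that the table matches the four dispositions in the text above it.

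Describe the result as differences in recorded characteristics between enrollees and each group. Do not present the refuser comparison as evidence about patients who would not consider taper.

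The cost is a few sentences and a revised table layout. The dispositions are already kept for the duration of the study and the variables already come from the data warehouse, so no new data collection is needed and no design figure changes.
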